5.8 Exploratory Analyses

6 INTERIM ANALYSES

No interim analyses were planned for this study.

7 CHANGES IN THE PLANNED ANALYSES

There were no changes to the planned analyses.

8 DEFINITIONS AND CONVENTIONS FOR DATA HANDLING

8.1 Pharmacokinetic Data Handling

8.1.1 Lower Limit of Quantification of E2814 Serum and Plasma concentration

The LLOQ of E2814 in serum and plasma is 1.00 ug/mL and in CSF is 1.00 ng/mL

8.1.2 BLQ Handling for Calculation of PK Parameters

While calculating PK parameters in WinNonlin, the following criteria should be used.

- Following single (or the first) dose, BLQ value(s) at pre-dose and up to the first quantifiable concentration, above lower limit of quantification (LLOQ), should be replaced with zero.
- Following the first quantifiable concentration, a single BLQ between 2 quantifiable concentrations should be set to “missing.”
- Following the first quantifiable concentration, if a quantifiable concentration is followed by 2 consecutive BLQs in terminal phase, all subsequent quantifiable concentrations should be assigned to “missing.”

8.1.3 BLQ Handling for Developing Concentration-Time Profiles

When developing individual concentration-time profiles, BLQ values are replaced with:

- Zero for time points prior to the first non-zero concentration following single (or first) dosing in a linear plot
- “Missing” for time points after the first non-zero concentration following single (or first) dosing in a linear plot
- “Missing” for all BLQ values in a semi-logarithmic plot

When calculating the mean (or median) value for the concentration at a given time point, all BLQ values are assigned as zero. If the proportion of values reported as BLQ is more than 50% or the calculated mean (or median) value is less than LLOQ at a time point, the value of mean (or median) is treated as:

- Zero for time points prior to the first non-zero mean (or median) concentration following single (or first) dosing in a linear plot
- “Missing” for time points after the first non-zero mean (or median) concentration following single (or first) dosing in a linear plot
- “Missing” for all BLQ values in a semi-logarithmic plot

8.1.4 Handling of Anomalous Concentration Values

Anomalous values are those that are inconsistent with known or expected PK behavior of the drug but are not defined on the basis of statistical tests for outliers. Individual concentrations deemed to be anomalous can be excluded from the PK analysis and median and mean profiles. Anomalous values will be identified in the CSR. Clear justification must be provided in the CSR for exclusion of any data.

8.1.5 General Rules for Presentation of Drug Concentrations and PK Parameters

When presenting individual/raw (raw, hereafter) values and summary statistics, the following rule will be applied: for drug concentrations and concentration-dependent pharmacokinetic parameters, all summary statistics (mean, median, geometric mean, SD, and CV) will have 3 significant digits. For t_{max} and t_{lag} , raw values and median have fixed 2 decimal places.

Typical variable	Standard Unit (depends on compound)	N	Digit rule	Raw Minimum Maximum	Mean Median	SD	Geometric Mean	CV (%)
E2814 concentration	Plasma/serum ug/mL CSF ng/mL	X	Significant digits	3	3	3	-	-
C_{max} , C_{min}	Plasma/serum ug/mL CSF ng/mL	X	Significant digits	3	3	3	3	3

Typical variable	Standard Unit (depends on compound)	N	Digit rule	Raw Minimum Maximum	Mean Median	SD	Geometric Mean	CV (%)
t_{max} , t_{lag}^a	h	X	Fixed decimal places	2	2	-	-	-
λ_z	1/h	X	Significant digits	3	3	3	3	3
$t_{1/2}$	h	X	Significant digits	3	3	3	3	3
AUC	Plasma/serum ug·h/mL CSF ng.h/mL	X	Significant digits	3	3	3	3	3
%AUC _{ex}	%	X	Significant digits	3	3	3	3	3
CL	L/h	X	Significant digits	3	3	3	3	3
V _d	L	X	Significant digits	3	3	3	3	3
MRT	h	X	Significant digits	3	3	3	3	3

a: Mean, SD, geometric mean and CV will not be calculated for t_{max} and t_{lag} .

CV(%) = $\sqrt{\exp[SD^2 \text{ of log transformed data}]-1} \times 100$

8.1.6 General Rules for Presentation of PD Parameters

Summary statistics for the PD data will be presented to 3 significant digits.

For the PD biomarker assays, the LLOQ and ULLQ values will be provided together with the data.

When producing TLGs for the PD data, BLQ and ALQ values in tables and figures will be handled as follows:

For Free MTBR-Tau species (including, Free MTBR-Tau-299 and Free MTBR-Tau-354) and other PD biomarkers apart from Bound MTBR-tau species,

- BLQ values will be replaced with $0.5 \times \text{LLOQ}$ and ALQ values replaced with $2 \times \text{ULQ}$.

For Bound MTBR-tau species (including, Bound MTBR-Tau-299 and Bound MTBR-Tau-354):

- A concentration that is BLQ is assigned a value of zero if it is pre-dose or if it occurs in a profile after dosing at time zero and before the first measurable concentration.
- If a BLQ value occurs after a measurable concentration and is followed by a value above the lower limit of quantification, then the LLOQ/2 is used.
- If a BLQ value occurs after the last quantifiable concentration it is treated as LLOQ/2.

For listings no derivations are required therefore values of BLQ and ALQ will be presented.

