9.7.1.1 Study Endpoints

9.7.1.1.1 PRIMARY ENDPOINTS

[figure not shown]
- Incidence of treatment-emergent adverse events (TEAEs) and SAEs, laboratory parameters, vital signs, and ECGs
- Change from baseline in CSF free and bound MTBR-tau and total MTBR-tau at 12 weeks in Cohort A (revised per Amendment 03)

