5.1.4 Pharmacodynamic (PD) Endpoint(s)

- Change from baseline in CSF free and bound MTBR-tau and total MTBR-tau post-treatment
- Change from baseline in CSF biomarkers ^{CCI} [REDACTED]
- Change from baseline in tau PET signal

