5.5.2 Pharmacodynamic Analyses

The PD Analysis Set will be used for both the listings and summaries of all biomarker CSF and plasma measurements ^{CC1}

Biomarker measurements (fluid and imaging) and change from baseline will be summarized by time point and dose and presented graphically.

These analyses will be done for CSF, plasma and serum. Dose-response relationships will be evaluated.

CCI

Derivations required for BLQ (below the limit of quantification) and ALQ (above the limit of quantification) values are described in Section 8.1.6 below.

Other exploratory biomarker analyses may be performed and reported separately, and the results will not be included in the clinical study report. Details of these analyses would be described in a separate analysis plan.

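### Do the rules in SAP 8.1.6 for MTBR-tau results outside the assay range distort the Week 12 target-engagement summary?

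*SAP*

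**What the plan says.** One primary endpoint in Protocol 9.7.1.1.1 is "Change from baseline in CSF free and bound MTBR-tau and total MTBR-tau at 12 weeks in Cohort A". SAP 5.1.4 words the endpoint more widely, as "Change from baseline in CSF free and bound MTBR-tau and total MTBR-tau post-treatment", so later visits and Cohort B are summarised too. SAP 5.5.2 points to one place for results outside the assay range: "Derivations required for BLQ (below the limit of quantification) and ALQ (above the limit of quantification) values are described in Section 8.1.6 below".

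SAP 8.1.6 then states that "BLQ and ALQ values in tables and figures will be handled as follows":

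- **Free MTBR-tau and every other PD marker except bound species.** BLQ is set to half the lower limit, with "ALQ values replaced with" twice the upper limit.
- **Bound MTBR-tau, BLQ.** The value is zero if the sample is pre-dose, or "if it occurs in a profile after dosing at time zero and before the first measurable concentration". It is LLOQ/2 if it falls between measurable values. At the end of a series the rule is: "If a BLQ value occurs after the last quantifiable concentration it is treated as LLOQ/2".
- **Bound MTBR-tau, ALQ.** Nothing is stated.

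Listings show BLQ and ALQ as reported. The PD assay limits are not printed in the SAP; the LLOQ and upper-limit "values will be provided together with the data". SAP Section 5 plans mean, SD, median, minimum and maximum. Programming rules and table shells are separate documents (SAP 9 and 11).

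**The concern.** Three features look wrong.

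1. The code for a bound BLQ result depends on the subject's earlier samples. A subject with BLQ, then a measurable value, then BLQ is recorded as 0, value, LLOQ/2. That is an apparent rise of LLOQ/2 between two identical assay results.
2. Setting ALQ to twice the upper limit puts a jump of one ULOQ at the limit. It can create, enlarge, shrink or hide a within-subject change.
3. The opening sentence of 8.1.6 promises handling of both BLQ and ALQ, but the bound-species bullets deal only with BLQ.

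The endpoint is primary and the groups are small: up to 8 subjects in Cohort A and up to 5 in Cohort B. One substituted value therefore moves a mean or SD visibly, and an ALQ code can become the reported maximum.

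**Working it through.** **Inputs.** The rules are from SAP 8.1.6 and the group sizes (8 and 5) from SAP Section 4. Protocol 9.5.1.3.1 gives Cohort A CSF on Day 1 and Day 84, then Day 169 onward, and Cohort B CSF on Day 1, Week 24 and Week 52. No PD assay limit or BLQ/ALQ frequency is given, so sizes are per affected sample, in units of LLOQ or ULOQ. The SAP states no figure to reproduce.

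**Bound BLQ at Week 12.** Only Day 1 and Day 84 exist in CSF. Write B for BLQ and M for a measurable value m.

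| Day 1, Day 84 | Coded | Change |
|---|---|---|
| B, B | 0, 0 | 0 |
| B, M | 0, m | m |
| M, B | m, LLOQ/2 | LLOQ/2 − m |
| M, M | as measured | as measured |

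Only M, B would differ under a code of 0. The effect on an 8-subject mean is 0.5/8 = 0.0625 LLOQ per such subject.

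**Bound BLQ after Week 12.** The apparent rise needs B, M, B. It adds 0.5/8 = 0.0625 LLOQ to an 8-subject mean, or 0.5/5 = 0.10 LLOQ to a 5-subject mean. In CSF the earliest it can occur is Day 169 in Cohort A and Week 52 in Cohort B. If bound tau is also measured in plasma, a third sample exists by Day 15.

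**What a single constant would do.**

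- LLOQ/2 throughout lowers each B-to-M rise by LLOQ/2. With k such subjects the 8-subject mean falls by 0.5k/8: 0.0625 LLOQ for k = 1 and 0.5 LLOQ for k = 8. B-to-M is the pattern a working drug should produce.
- 0 throughout leaves those rises alone but understates a BLQ result that follows a measurable one, by 0.0625 LLOQ in the Week 12 mean per M, B subject.

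**ALQ for non-bound markers.** Take a true value x above the limit, in ULOQ units. The error is 2 − x under the plan and 1 − x under a cap at ULOQ. The two are equal in size at x = 1.5. The values below are chosen for illustration; the last two columns are (coded change − true change)/8.

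| True values | True change | 2 x ULOQ | Cap | Mean shift, 2 x ULOQ | Mean shift, cap |
|---|---|---|---|---|---|
| 1.05 to 0.95 | −0.10 | −1.05 | −0.05 | −0.119 | +0.006 |
| 3.0 to 0.9 | −2.10 | −1.10 | −0.10 | +0.125 | +0.250 |
| 1.1 to 1.5 | +0.40 | 0 | 0 | −0.050 | −0.050 |
| 0.9 to 1.8 | +0.90 | +1.10 | +0.10 | +0.025 | −0.100 |

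The coded value never decreases as the true value rises, so neither rule can reverse the sign of a within-subject change.

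**The word pre-dose.** Protocol 9.5.1.3.1 also labels the Day 84 CSF sample predose. Read literally, a Day 84 BLQ after a measurable Day 1 meets both the zero bullet and the LLOQ/2 bullet. The literal reading would mean that LLOQ/2 never applied to any CSF sample the protocol calls predose, which cannot be the intent. The zero bullet also counts from dosing at time zero. Pre-dose therefore means before the first dose. The two readings differ only for M, B, by the same 0.0625 LLOQ.

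**The case for a change.** The best case for a change runs as follows. These rules govern a primary endpoint, and two programmers could code one sample differently. Dose-response is to be evaluated and PK/PD is judged from plots, where substituted points appear as if measured. Dosing should raise bound tau, so the missing upper-limit rule lies where values may go. The remedy is cheap: one constant, a sensitivity summary and a count of substitutions.

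Some of this stands. The bound ALQ line is missing and pre-dose is undefined. A count of substituted values beside each summary would help readers, and nothing in the visible text asks for one, although part of SAP 5.5.2 is redacted and the shells are separate.

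The rest does not carry. Protocol 9.5.1.3.2 treats free and bound MTBR-tau as the target-engagement measure. A BLQ bound result before any drug is then naturally 0, while LLOQ/2 is a fair estimate once binding has been seen. Zero before the first quantifiable value is also the SAP's convention for drug concentrations (8.1.2). Twice the upper limit mirrors half the lower limit in the same bullet. Each replacement constant does better in some cases and worse in others.

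**Conclusion.** No change to the plan follows. The observations about the text are correct, but the bound BLQ rule is a reasonable trade-off, the ALQ constant has no uniformly better rival, and the bound ALQ gap is missing detail. Analysts can settle that gap by applying the rule used for the other PD markers, recorded in the programming specifications before the data are summarised.

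At Week 12 the bound BLQ rule affects only subjects who are measurable before drug and BLQ after three infusions, at 0.0625 LLOQ each in a mean of 8. The later apparent rise requires binding to be lost while dosing escalates (Cohort A) or stays constant (Cohort B). That is not the expected course, though an early-termination sample could show it. The analysis is descriptive, medians are planned and listings keep the reported results, so a reader can see any substitution.

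This rests on three assumptions: bound MTBR-tau is mostly unmeasurable before the first dose, pre-dose means before the first dose, and results outside the assay range are not common. The documents do not settle the first or the third. Nor do they say whether total MTBR-tau is measured directly, in which case the non-bound rule covers it, or derived from free and bound. Frequent ALQ results would make the means depend on the constant chosen, and the medians and listings should then lead the interpretation.

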9 PROGRAMMING SPECIFICATIONS

The rules for programming derivations and dataset specifications are provided in separate documents.

10 STATISTICAL SOFTWARE

Analysis will be performed using SAS (release 9.4 or newer), Phoenix WinNonlin (version 6.4 or newer) and Microsoft Excel (2010 or newer).

11 MOCK TABLES, LISTINGS, AND GRAPHS

The study TLG shells will be provided in a separate document, which will show the content and format of all tables, listings, and graphs in detail.

13 APPENDICES

13.1 Derivations for Clinical and Cognitive Assessments.

Geriatric Depression Scale: Short Form

1. Are you basically satisfied with your life? **YES / NO**
2. Have you dropped many of your activities and interests? **YES / NO**
3. Do you feel that your life is empty? **YES / NO**
4. Do you often get bored? **YES / NO**
5. Are you in good spirits most of the time? **YES / NO**
6. Are you afraid that something bad is going to happen to you? **YES / NO**
7. Do you feel happy most of the time? **YES / NO**
8. Do you often feel helpless? **YES / NO**
9. Do you prefer to stay at home, rather than going out and doing new things? **YES / NO**
10. Do you feel you have more problems with memory than most? **YES / NO**
11. Do you think it is wonderful to be alive now? **YES / NO**
12. Do you feel pretty worthless the way you are now? **YES / NO**
13. Do you feel full of energy? **YES / NO**
14. Do you feel that your situation is hopeless? **YES / NO**
15. Do you think that most people are better off than you are? **YES / NO**

Answers in bold indicate depression. Score 1 point for each bolded answer.

A score > 5 points is suggestive of depression.

A score ≥ 10 points is almost always indicative of depression

For each of the following assessments, (Functional assessment scale [FAS], Neuropsychiatric Inventory–Questionnaire [NPI-Q], Memory Assessment Questionnaire [MAC-Q]), sum the individual component scores to generate a summary score for each. If a response is NA or unknown, treat as missing. If at any given visit, the number of missing items within a questionnaire is less than 30% of the total number of items, then the score for this component at this visit will be calculated as the sum of the non-missing items multiplied by the ratio of the total number of items to the number of the non-missing items. If the number of missing items is equal to or greater than 30%, then the score at this visit is considered missing.

Values captured within the FAS as ‘not applicable (e.g., never did)’ (NA) will be treated as missing.

13.2 Sponsor's Grading for Determining Markedly Abnormal Laboratory Results

The following table of Sponsor's Grading for Laboratory Values is copied from the protocol, Appendix 1.

Sponsor's Grading for Laboratory Values

	Grade 1	Grade 2	Grade 3	Grade 4
BLOOD/BONE MARROW				
Hemoglobin	<LLN – 10.0 g/dL <LLN – 100 g/L <LLN – 6.2 mmol/L	<10.0 – 8.0 g/dL <100 – 80 g/L <6.2 – 4.9 mmol/L	<8.0 g/dL <80 g/L <4.9 mmol/L; transfusion indicated	life-threatening consequences; urgent intervention indicated
Leukocytes (total WBC)	<LLN – 3.0×10 ⁹ /L <LLN – 3000/mm ³	<3.0 – 2.0×10 ⁹ /L <3000 – 2000/mm ³	<2.0 – 1.0×10 ⁹ /L <2000 – 1000/mm ³	<1.0×10 ⁹ /L <1000/mm ³
Lymphocytes	<LLN – 800/mm ³ <LLN – 0.8×10 ⁹ /L	<800 – 500/mm ³ <0.8 – 0.5×10 ⁹ /L	<500 – 200/mm ³ <0.5 – 0.2×10 ⁹ /L	<200/mm ³ <0.2×10 ⁹ /L
Neutrophils	<LLN – 1.5×10 ⁹ /L <LLN – 1500/mm ³	<1.5 – 1.0×10 ⁹ /L <1500 – 1000/mm ³	<1.0 – 0.5×10 ⁹ /L <1000 – 500/mm ³	<0.5×10 ⁹ /L <500/mm ³
Platelets	<LLN – 75.0×10 ⁹ /L <LLN – 75,000/mm ³	<75.0 – 50.0×10 ⁹ /L <75,000 – 50,000/mm ³	<50.0 – 25.0×10 ⁹ /L <50,000 – 25,000/mm ³	<25.0×10 ⁹ /L <25,000/mm ³
METABOLIC/LABORATORY				
Albumin, serum- low (hypoalbuminemia)	<LLN – 3 g/dL <LLN – 30 g/L	<3 – 2 g/dL <30 – 20 g/L	<2 g/dL <20 g/L	life-threatening consequences; urgent intervention indicated
Alkaline phosphatase	>ULN – 2.5×ULN if baseline was normal; 2.0 – 2.5×baseline if baseline was abnormal	>2.5 – 5.0×ULN if baseline was normal; >2.5 – 5.0×baseline if baseline was abnormal	>5.0 – 20.0×ULN if baseline was normal; >5.0 – 20.0×baseline if baseline was abnormal	>20.0×ULN if baseline was normal; >20.0×baseline if baseline was abnormal
ALT	>ULN – 3.0×ULN if baseline was normal; 1.5 – 3.0×baseline if baseline was abnormal	>3.0 – 5.0×ULN if baseline was normal; 3.0 – 5.0×baseline if baseline was abnormal	>5.0 – 20.0×ULN if baseline was normal; >5.0 – 20.0×baseline if baseline was abnormal	>20.0×ULN if baseline was normal; >20.0×baseline if baseline was abnormal
AST	>ULN – 3.0×ULN if baseline was normal; 1.5 – 3.0×baseline if baseline was abnormal	>3.0 – 5.0×ULN if baseline was normal; 3.0 – 5.0×baseline if baseline was abnormal	>5.0 – 20.0×ULN if baseline was normal; >5.0 – 20.0×baseline if baseline was abnormal	>20.0×ULN if baseline was normal; >20.0×baseline if baseline was abnormal
Bilirubin (hyperbilirubinemia)	>ULN – 1.5×ULN if baseline was normal; 1.0 – 1.5×baseline if baseline was abnormal	>1.5 – 3.0×ULN if baseline was normal; 1.5 – 3.0×baseline if baseline was abnormal	>3.0 – 10.0×ULN if baseline was normal; 3.0 – 10.0×baseline if baseline was abnormal	>10.0×ULN if baseline was normal; >10.0×baseline if baseline was abnormal
Calcium, serum-low (hypocalcemia)	<LLN – 8.0 mg/dL <LLN – 2.0 mmol/L Ionized calcium <LLN - 1.0 mmol/L	<8.0 – 7.0 mg/dL <2.0 – 1.75 mmol/L Ionized calcium <1.0 - 0.9 mmol/L; symptomatic	<7.0 – 6.0 mg/dL <1.75 – 1.5 mmol/L Ionized calcium <0.9 - 0.8 mmol/L; hospitalization indicated	<6.0 mg/dL <1.5 mmol/L Ionized calcium <0.8 mmol/L; life-threatening consequences
Calcium, serum-high (hypercalcemia)	>ULN – 11.5 mg/dL >ULN – 2.9 mmol/L Ionized calcium >ULN - 1.5 mmol/L	>11.5 – 12.5 mg/dL >2.9 – 3.1 mmol/L Ionized calcium >1.5 - 1.6 mmol/L; symptomatic	>12.5 – 13.5 mg/dL >3.1 – 3.4 mmol/L Ionized calcium >1.6 - 1.8 mmol/L; hospitalization indicated	>13.5 mg/dL >3.4 mmol/L Ionized calcium >1.8 mmol/L; life- threatening consequences

Sponsor's Grading for Laboratory Values

	Grade 1	Grade 2	Grade 3	Grade 4
Cholesterol, serum-high (hypercholesterolemia)	>ULN – 300 mg/dL >ULN – 7.75 mmol/L	>300 – 400 mg/dL >7.75 – 10.34 mmol/L	>400 – 500 mg/dL >10.34 – 12.92 mmol/L	>500 mg/dL >12.92 mmol/L
Creatinine	>ULN – 1.5×ULN	>1.5 - 3.0×baseline; >1.5 – 3.0×ULN	>3.0×baseline; >3.0 – 6.0×ULN	>6.0×ULN
Fibrinogen plasma-low	>125 - 175 mg/dL	>80 – 125 mg/dL	50- 80 mg/dL	<50 mg/dL
Fibrinogen plasma-high	425 - 500 mg/dL	>500 - 600 mg/dL	>600 - 700 mg/dL	> 700 mg/dL
GGT (γ -glutamyl transpeptidase)	>ULN – 2.5×ULN if baseline was normal; 2.0 - 2.5 x baseline if baseline was abnormal	>2.5 – 5.0×ULN if baseline was normal; >2.5 - 5.0 x baseline if baseline was abnormal	>5.0 – 20.0×ULN if baseline was normal; >5.0 - 20.0 x baseline if baseline was abnormal	>20.0×ULN if baseline was normal; >20.0 x baseline if baseline was abnormal
Glucose, serum-high (hyperglycemia)	Abnormal glucose above baseline with no medical intervention	Change in daily management from baseline for a diabetic; oral antihyperglycemic agent initiated; workup for diabetes	Insulin therapy initiated; hospitalization indicated	life-threatening consequences; urgent intervention indicated
Glucose, serum-low (hypoglycemia)	<LLN – 55 mg/dL <LLN – 3.0 mmol/L	<55 – 40 mg/dL <3.0 – 2.2 mmol/L	<40 – 30 mg/dL <2.2 – 1.7 mmol/L	<30 mg/dL <1.7 mmol/L life-threatening consequences; seizures
Phosphate, serum-low (hypophosphatemia)	Laboratory finding only and intervention not indicated	Oral replacement therapy indicated	Severe or medically significant but not immediately life-threatening; hospitalization or prolongation of existing hospitalization indicated	life-threatening consequences
Potassium, serum-high (hyperkalemia)	>ULN – 5.5 mmol/L	>5.5 – 6.0 mmol/L	>6.0 – 7.0 mmol/L hospitalization indicated	>7.0 mmol/L life-threatening consequences
Potassium, serum-low (hypokalemia)	<LLN – 3.0 mmol/L	<LLN – 3.0 mmol/L; symptomatic; intervention indicated	<3.0 – 2.5 mmol/L hospitalization indicated	<2.5 mmol/L life-threatening consequences
Sodium, serum-high (hypernatremia)	>ULN – 150 mmol/L	>150 – 155 mmol/L; intervention initiated	>155 – 160 mmol/L hospitalization indicated	>160 mmol/L life-threatening consequences
Sodium, serum-low (hyponatremia)	<LLN – 130 mmol/L	125-129 mmol/L and asymptomatic	<125 – 129 mmol/L symptomatic; 120-124 mmol/L regardless of symptoms	<120 mmol/L life-threatening consequences
Triglyceride, serum-high (hypertriglyceridemia)	150 – 300 mg/dL 1.71 – 3.42 mmol/L	>300 – 500 mg/dL >3.42 – 5.7 mmol/L	>500 – 1000 mg/dL >5.7 – 11.4 mmol/L	>1000 mg/dL >11.4 mmol/L life-threatening consequences

Sponsor's Grading for Laboratory Values

	Grade 1	Grade 2	Grade 3	Grade 4
Uric acid, serum-high (hyperuricemia)	>ULN without physiologic consequences	N/A	>ULN with physiologic consequences	life-threatening consequences

ALT = alanine aminotransferase (serum glutamic pyruvic transaminase), AST = aspartate aminotransferase (serum glutamic oxaloacetic transaminase), N/A = not applicable, LLN = lower limit of normal, ULN = upper limit of normal, WBC = white blood cell.

Based on Common Terminology Criteria for Adverse events (CTCAE) Version 5.0. Published: 27 Nov 2017.

SIGNATURE PAGE

Author:

PPD
Primary Statistician
PPD
Eisai Ltd

Date

Approval:

PPD
PPD
Translational Science Biostatistics
PPD
Eisai Inc.

Date

Study Director

PPD
PPD
Eisai Inc.

Date
